The *Dominic-R* is appropriate for both clinical and epidemiologic purposes with strong test - re-test reliability with younger children (i.e., 6 – 11 years of age; Valla et al., 1997). Instead of being organized in diagnostic modules, symptoms have been randomly mixed to avoid the halo effect, and normal situations are intermixed with DSM-III-R abnormal behaviours. The Dominic character may be interpreted either as a boy or a girl to allow assessment of both genders. The pictorial format is in keeping with best clinical practice and with the cognitive abilities of young children, and at the same time complies with the epidemiological requirement for standardized assessment by lay interviewers.

We will analyze the results for each subscale independently. We predict a significant effect for birth weight (corrected for gestational age) on scores for the attention deficit/hyperactivity disorder, depression/dysthymia, overanxious disorder, separation anxiety disorder and simple phobias, reflecting the known relations between fetal growth and emotional function in childhood. We will also provide preliminary analyses on the scales for conduct disorder and oppositional defiant disorder for which there is to date very little data linking prenatal development to outcomes. We also predict that the effects of fetal growth will be moderated by the quality of postnatal mother – child relation such that the statistical relation between birth weight and clinical outcome will be non-significant in children with a high quality of maternal care and with a secure level of attachment. This finding will be represented as a significant statistical interaction (see below).

NEPSY: A Developmental Neuropsychological Assessment (15 minutes)

The NEPSY consists of a series of neuropsychological subtests offering a comprehensive assessment of neuropsychological development in children 3-12 years of age. These subtests enable the examiner to evaluate and explore the deficiencies that interfere with the child's learning. Some subscales (Sensory motor functions, Visuospatial processing) of the NEPSY have been accepted by the ERB for the 48 month assessment. But for the 72 month visits, we will focus on the language domain including the following subtests: Verbal Fluency (speeded naming), repetition of pseudowords, phonological processes.

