The observations of parents and teachers provide a wealth of information about a child's behavior that is directly relevant to an understanding of that child's executive functioning. The BRIEF-P is the first standardized rating scale designed to specifically measure the range of behavioral manifestations of executive function in preschool-aged children--thus facilitating intervention at earlier stages of development. The BRIEF-P consists of a single Rating Form used by parents, teachers, and day care providers to rate a child's executive functions within the context of his/her everyday environments--home and preschool. The original Behavior Rating Inventory of Executive Function™ (BRIEF™) was the basis for the development of the BRIEF-P. Consequently, the BRIEF-P is an ecologically valid and efficient tool for screening, assessing, and monitoring a young child's executive functioning and development.

Children

Attention Tests: CANTAB (60 minutes)

This measure has already been accepted by the Douglas Hospital Ethic Board for the 60 month assessment. For the 72 mo assessment, we will use the same subtests as used in the 60 month protocol. The CANTAB battery will be performed during the 2 separation periods of the Strange Situation. During this separation, the mothers will be asked to fill in questionnaires in a separate room.

Nutritional status: Body weight and body fat percentage will be measured using the Tanita® BF 625 scale (foot to foot bioelectrical impedance) which functions as a portable regular scale. Height will be measured using a stadiometer. These measures have already been accepted by the Douglas Hospital Ethic Board for the 48-month assessment.

Analyses

In accordance with CIHR policy on identifying gender effects, analyses will be stratified by gender. Statistical significance will be corrected for multiple comparisons where appropriate. The sample size (currently ~600 children are enrolled in the MAVAN study) is well above the range of published interaction studies [e.g., 3,4,7-9,11], which typically include 100-150 subjects. As per the comments on the previous submission, we focus on the analyses of the new measures. Please note that the MAVAN Project has been funded by CIHR (2009-2014; Behavioural Sciences B) to examine birth weight x genotype interaction effects on cognitive development using the CANTAB measures described here as well as the Connors Rating Scale ([name] (PI) and [name] (Co_PI)).

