Hypothesis 1: The relation between birth weight and measures of childhood mental health will be moderated by the quality of post-natal maternal care. We will focus on two outcomes measures, the Connors questionnaire and the DOMINIC-R questionnaire. We predict a significant interaction between birth weight corrected for gestational age x child attachment (secure versus insecure). Birth weight will be examined as a categorical variable using the following percentile groupings for birth weight for gestational age (0-20%, 21-40% and 41-70%). These percentiles are calculated using contemporary Canadian norms (Kramer, 2001). We have previously used these groupings to show significant effects of birth weight on tests of attention and impulse control. The results will be analyzed using a two way ANOVA (birth weight class) x attachment category, with a predicted interaction effect (post-hoc analyses) such that birth weight effects are apparent only amongst children showing insecure attachment. Subsequent ANCOVA's could be used to test the effects of possible moderators, including measures of sleep quality, which can affect mood as well as cognitive performance.

The same analysis will be applied to the results of the Connors Rating Scale, which is included as the current standard rating scale measure for symptoms associated with the Attentional Deficit Hyperactivity Disorder. The use of this measure also allows us to correlate a standard parent/teacher rating scale to the self-report measures of the child. Likewise, we predict a similar birth weight x child attachment interaction effect on the BRIEF (Behavior Rating Inventory of Executive Function) measure of executive function. A strength in this approach is that of the overlapping measures. While this implies greater number of statistical tests, this is the opportunity for the establishment of converging evidence should the predict interaction emerge in each of these analyses.

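### The interaction test can show that the birth-weight effect differs by attachment, but the plan's further prediction of no effect in secure children rests on a non-significant subgroup result, which cannot show absence

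*Protocol*

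**What the plan says.** In the Protocol, under Measures (DOMINIC-R), the moderation prediction is put in terms of a subgroup test: "the statistical relation between birth weight and clinical outcome will be non-significant in children with a high quality of maternal care". The same sentence adds secure attachment. The next sentence supplies the formal criterion: "This finding will be represented as a significant statistical interaction (see below".

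Under Analyses, Hypothesis 1, the interaction comes first: "We predict a significant interaction between birth weight corrected for gestational age x child attachment (secure versus insecure". It is tested in a two-way ANOVA using three birth-weight-for-gestational-age percentile classes, "0-20%, 21-40% and 41-70". The subgroup comparisons follow, "with a predicted interaction effect (post-hoc analyses) such that" "birth weight effects are apparent only amongst children showing insecure attachment". The same analysis is applied to the Conners scale, and a similar interaction is predicted for the BRIEF.

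The opening of Analyses adds that "analyses will be stratified by gender" and gives the sample as "currently ~600 children are enrolled in the MAVAN study". For this interaction and for the secure subgroup, the documents give no power, effect size, confidence-interval rule or margin for calling an effect absent. The only power figure in the 72-month Protocol concerns gene by environment effects. The power calculation in the 2004 combined protocol and SAP concerns maternal sensitivity and infant cortisol.

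**The concern.** Two claims are run together. One is that the birth-weight effect differs between secure and insecure children, which the interaction tests. The other is that the effect is absent in secure children. For this the plan offers only a non-significant post-hoc result. That result is expected when the effect is gone, and also when the effect is reduced and the subgroup is too small to detect it.

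The distinction matters for use of the results. The Introduction of the 2004 document intends the study as a basis for early intervention programmes, and whether good care reduces fetal risk or removes it is a different message for that purpose. The Protocol's background already describes an earlier moderation finding as no relation in the high-care group. That shows how such results may be worded, but it does not settle how this one will be reported.

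**Working it through.** There is no figure in the plan to reproduce, so this is an illustration.

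**Inputs from the documents.** Three classes spanning 20, 20 and 30 percentile points, with nothing above the 70th (Protocol, Hypothesis 1). About 600 enrolled (Analyses). Non-completion of 13% (2004 document, Statistical analysis), used as a scenario only.

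**Assumptions.** Class sizes 20:20:30. Linear trend across classes, SD 1, with d = lowest minus highest class. Alpha 0.05 two-sided, since the plan states none for this analysis. 60% secure (range 50 to 65%), since the share is not stated. Analysed N: 600; 420 (= 0.70 × 600, if the sample follows the norms and children above the 70th percentile are left out); 365 (= 420 × 0.87).

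**Step 1: power within secure children.** With class shares 2/7, 2/7, 3/7 and means d, d/2, 0, the overall mean is 0.4286d. The noncentrality of the three-class F-test is

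λ = n × d² × (2/7 × 0.5714² + 2/7 × 0.0714² + 3/7 × 0.4286²) = 0.1735 × n × d².

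For n = 252 (60% of 420) and d = 0.25, λ = 2.73.

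| Analysed N | Secure n | Power, d = 0.2 | d = 0.25 | d = 0.3 | d = 0.5 |
|---|---|---|---|---|---|
| 600 | 360 | 27% | 40% | 55% | 95% |
| 420 | 252 | 20% | 29% | 41% | 85% |
| 365 | 219 | 18% | 26% | 36% | 79% |
| one sex of 420 | 126 | 12% | 16% | 22% | 53% |

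At N = 420, varying the secure share over 50 to 65% moves power at d = 0.3 between 34% and 43%.

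**Step 2: what the interaction test protects against.** With equal true effects (d = 0.3 in both groups), simulation at N = 365 to 600 gives the pattern 'insecure significant, secure not' in 16 to 17% of studies. Requiring a significant interaction as well as a non-significant secure group leaves about 2%.

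**Step 3: what it does not protect against.** Half the effect remains (d = 0.5 insecure, 0.25 secure), compared with full removal (0.5 and 0). 100,000 simulated studies per row:

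| N | Interaction significant, 0.5 vs 0.25 | Secure non-significant among those | Interaction significant, 0.5 vs 0 | Secure non-significant among those |
|---|---|---|---|---|
| 600 | 18% | 81% | 60% | 95% |
| 420 | 14% | 85% | 45% | 94% |
| 365 | 13% | 87% | 39% | 93% |

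Shorter runs of the half-effect case gave 82 to 88%; the difference is simulation error. With 50 to 65% secure the range is 79 to 87%.

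Among studies with a significant interaction, then, the non-significant secure result is nearly as common when half the effect remains as when none does. At N = 420 the ratio is 0.94/0.85, about 1.1. The interaction cannot fill the gap, because its power depends only on the difference between effects. At N = 365, effects of 0.8 and 0.3 give a significant interaction in 39% of studies, the same as 0.5 and 0, and 82% of those have a non-significant secure group.

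**Step 4: precision available.** The 95% half-width for lowest versus highest class in secure children is 1.96 × √(1/n_low + 1/n_high). At N = 420 this is 1.96 × √(1/72 + 1/108) = 0.30 SD. It is 0.25 SD at N = 600, 0.32 SD at N = 365 and 0.42 SD for one sex of 420. An estimate of exactly zero would leave 0.25 SD inside the interval at N = 420 and 365, and at its edge at N = 600.

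**The case against.** A reader might infer that the plan defines buffering as a non-significant result in secure children, so that poor power in that group would by itself count as proof. The documents do not support that. The sentence straight after the DOMINIC-R prediction, and the Hypothesis 1 analysis, both rest on a significant interaction, and the subgroup comparisons are labelled post hoc. The plan therefore avoids the common error of inferring moderation from one significant and one non-significant subgroup. Step 2 shows the protection is real: about 2% against 16 to 17%.

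It is also fair to say that these passages state predictions and set no rule of interpretation. The documents nowhere say that an abolished effect will be claimed, or that absence will be judged separately within each gender. The secure share, effect sizes, alpha and analysed N used above are assumptions.

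All of that stands. What it does not answer is the step from a smaller effect to none. The predicted pattern includes that step, the only evidence named for it is a null test, and no interval or margin would let a reader tell the two apart. The low chance of a significant interaction under partial buffering (13 to 18%) does not help. It means the problem arises in interpreting a positive result, which is where it matters.

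**Conclusion.** The point holds in this limited form. The interaction is a sound formal test of Hypothesis 1 and guards against claiming moderation when the effects are equal. The further prediction, that birth weight has no effect in secure children, cannot be supported by a non-significant subgroup test. Under the stated assumptions, 81 to 87% of studies with a significant interaction would show a non-significant secure group even though half the effect remained. The exact percentage depends on the assumed effects, secure share and analysed number. The logical point does not. Analyses by gender roughly halve the secure group and make a null result likelier still, as would any multiplicity correction. What the design can support is a difference in effects, with the secure-group effect described by its interval.

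**What to change.** - Keep the birth-weight class by attachment interaction as the test of Hypothesis 1.
- Report the difference in birth-weight effects (lowest versus highest class, secure versus insecure) with its 95% confidence interval.
- Report the birth-weight effect in secure children with its 95% confidence interval, whether or not the interaction is significant. Selecting on a significant interaction favours samples with a low secure-group estimate: at N = 600 the non-significant share rises from 60% of all studies to 81% of those selected.
- Show results pooled over sexes beside the gender-stratified results that the plan adopts under its funder's policy. They should not replace them.
- Replace the non-significance and insecure-only criteria with 'smaller in secure children'. Claim absence only if the secure-group interval lies within a margin that the sponsor justifies in advance. The half-widths in Step 4 show that a narrow margin could not be met with this sample.

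This is a cheap improvement: a change of wording and some added intervals, with no new data. The downside is that the strong claim of no effect in secure children will probably not be supportable.

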impaired fetal growth, reflected in low birth weight for gestational age, predicts an increased risk for multiple disorders associated with emotional and cognitive function [1,2]. In the best studied case, that of Attentional Deficit Disorder, it is clear that the link lies between fetal growth and individual differences in attentional systems [3-5] and that the relationship cuts across the normal range of birth weights: the risk for inattention and ADD increases progressively as birth weight decreases, such that the effect of fetal development is not unique to a small population of very low birth weight children. Rather, cognitive development is related to the quality of fetal growth and development across the population. In studies with non-human primates, maternal stress results in attentional deficits in attentional deficits [6].

Although this issue has been less well clarified for other areas of psychopathology, there is emerging evidence for the association of birth weight with anxious and depressive symptomatology. Shyness, timidity, behavioural inhibition as well as negative and irritable temperament (greater frequency of negative emotional states) are positively related to the degree of growth restriction [7-9], while direct evidence of increased depressive symptoms have been found in children and adolescents with IUGR [1,9-11]. Likewise, maternal stress during gestation predicts both fetal growth restriction and negative temperament (irritability, negative emotionality) and anxiety in children [12,13]. Finally, prenatal glucocorticoid exposure, which directly produces in fetal growth retardation, is associated with an increased level of behavioural inhibition in humans [14,15].

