The NEPSY is used as an age-appropriate measure for child general IQ for use as a potential covariate for effects on child emotional/cognitive functions.

Child Attribution Style Interview (24 items)

The Child Attributional Style Interview (CASI) is a measure of attributional style in children aged five years old and older. The interactive interview consists of sixteen events, which are presented to the child as 8 and ½” X 11” illustrations, in a storybook format. The events are centered on a main character; matched on gender to the child interviewed. The events are equally divided on two domains: valence (positive and

negative theme), and interpersonal (parents and peers) and achievement. This creates the possibility of four sub-categories for analysis (i.e. positive-achievement, negative-interpersonal etc.). After the presentation of each event, the child is asked three questions for their level of internal, stable and global attributions for each event. For example, to ask about how the child might internalize the cause of the event the research assistant asks the child, "How much is the event *because* of you?". To answer each question the child moves an arrow on a sliding scale, along an isosceles triangle. The larger side of the triangle represents in the example above, "*more because* of me" and the narrow side represents "*less because* of me". The CASI takes approximately 30 minutes to administer, which includes two practice sessions and administration of the sixteen CASI events.

The measure has been validated in a sample of five to seven year old by Conley, Haines, Hilt and Metalsky (2001) in a prospective, longitudinal study. The internal consistency for the measure was found to be between .73-.82 in children aged five and .77-.82 in children aged seven. In line with the reformulated learned helplessness theory, the children's answers on the CASI and self-esteem predicted changes in depression scores in times of increased stress. It should be noted that Conley et al. (2001) found that the younger children were more likely to pick extreme ends for each domain. However, the researchers found that the children had no bias for one extreme over another.

Seventy-two month interview: Laboratory visit (135 minutes)

Mother-child interaction (120 minutes)

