are consistently associated with cognitive impairments; the existing data suggest that cognitive outcomes are more seriously compromised by growth restriction than by prematurity (Lagercrantz 1997). Studies using more global measures of cognitive development, such as IQ tests, reported significant impairments among IUGR children (e.g., Breslau et al. 1996; Fattal-Valevski et al. 1999; Leitner et al. 2000;). van der Reijden-Lakeman et al. (1997) found that at 2 years of age, IUGR children were impaired on tests of divided, focused and sustained attention. On such tests, the IUGR population was less accurate and more impulsive than controls. These findings suggest that low-birth weight children might be at greater risk for the development of Attentional Deficit Disorder (ADD). Indeed, the risk factors for IUGR, including maternal stress, maternal psychopathology, protein malnutrition, tobacco/alcohol consumption are identical to those for ADD. Likewise, maternal stress during gestation is a predictor of both fetal growth restriction and negative temperament (irritability, negative emotionality) and anxiety in children (O'Connor et al. 2000; Glover et al. 2002). Behavioural disorders, characterized by poor impulsive control, shyness, timidity and negative temperament (greater frequency of negative emotional states) are positively related to the degree of growth restriction (e.g., Szatmari et al. 1990; Pharoah et al. 1994; Sykes et al. 1997).

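### Using the 72-month NEPSY score as an IQ covariate in a birth-weight model would adjust for a likely consequence of birth weight; the plan should make models without it the main analysis

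*Protocol*

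**What the plan says.** The NEPSY paragraphs in the Measures section of the Protocol give the test one analytic role: "The NEPSY is used as an age-appropriate measure for child general IQ for use as a potential covariate" when effects on the child's emotional and cognitive functioning are analysed. They also narrow its content: "But for the 72 month visits, we will focus on the language domain including the following subtests" covering verbal fluency, pseudoword repetition and phonology. The test belongs to the 72-month assessment, the same wave as the outcomes.

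On the link between exposure and covariate, the Background and rationale of the Protocol states that "cognitive development is related to the quality of fetal growth and development across the population". The Combined protocol and SAP, in the introductory part on adverse perinatal environment, adds: "Studies using more global measures of cognitive development, such as IQ tests, reported significant impairments among IUGR children".

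On the effects under study, the Dominic-R paragraphs of the Protocol say "We predict a significant effect for birth weight (corrected for gestational age) on scores for the attention deficit/hyperactivity disorder" and several emotional scales. They also predict that "the statistical relation between birth weight and clinical outcome will be non-significant in children with a high quality of maternal care" and secure attachment.

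The Analyses section of the Protocol tests Hypothesis 1 by a two-way ANOVA of birth-weight class by attachment category and names no covariate. Follow-up ANCOVAs are optional. They give sleep quality as an example and do not mention NEPSY. For the attributional-style interview (CASI), the same section reasons that if the measure is a mediator, including it should shrink the predicted interaction.

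**The concern.** The exposure is birth weight. NEPSY is measured about six years later, and on the documents' own account the ability it stands for is related to fetal growth. A covariate in that position is likely to lie on the path from exposure to outcome. Conditioning on it changes the question from the effect of birth weight to the part of that effect not passing through cognitive ability.

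The Protocol applies this logic to CASI but not to NEPSY. It does not say in which models NEPSY might enter, whether the unadjusted model has priority, or how an adjusted estimate would be read. At stake are the birth-weight main effects and the slopes within attachment groups. The problem is sharpest for attention and executive outcomes, where NEPSY overlaps the outcome itself.

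**Working it through.** The documents give no figure for a NEPSY-adjusted analysis, so there is none to reproduce. The check is mediation algebra under assumed path sizes.

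**Main effect.** Let a be the effect of birth weight on NEPSY, b the effect of NEPSY on the outcome given birth weight, c the total effect of birth weight, and c′ the effect after adjustment. All are standardized, in absolute size, with the indirect and total effects taken to have the same sign.

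- NEPSY = a × birth weight + error
- Outcome = c′ × birth weight + b × NEPSY + error
- Hence c = c′ + a × b, and the share removed by adjustment is a × b / c.

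Assumed ranges: a from 0.1 to 0.3, b from 0.1 to 0.4, c from 0.15 to 0.30.

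| c | a = 0.1, b = 0.1 (ab = 0.01) | a = 0.2, b = 0.3 (ab = 0.06) | a = 0.3, b = 0.4 (ab = 0.12) |
|---|---|---|---|
| 0.15 | 7% | 40% | 80% |
| 0.20 | 5% | 30% | 60% |
| 0.30 | 3% | 20% | 40% |

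The range is 3% (0.01/0.30) to 80% (0.12/0.15). The upper end needs birth weight to predict NEPSY twice as strongly as it predicts the outcome (0.30 against 0.15).

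**Interaction.** Let the first path be a_I in insecure and a_S in secure children, with NEPSY entered as one covariate with a common slope b. Adjustment removes b × a_I from the insecure slope and b × a_S from the secure slope, so it removes b × (a_I − a_S) from the interaction.

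- Common link (a_I = a_S): nothing is removed.
- Link in insecure children only (a_S = 0), with a direct interaction of 0.20: the share removed is ab / (0.20 + ab). For a = 0.1 and b = 0.2 this is 0.02/0.22 = 9%; for a = 0.3 and b = 0.4 it is 0.12/0.32 = 38%.

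**Simulation.** The set-up was 400,000 children, three birth-weight classes, 60% secure (assumed), a direct birth-weight slope of −0.20 in insecure children and none in secure children, a from 0.1 to 0.3, and b of 0.2 or 0.4.

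- Common link: the interaction changed by 1% or less. The secure slope moved from between −0.02 and −0.12 to about 0, and the insecure slope from between −0.22 and −0.32 to about −0.20.
- Link in insecure children only: 8% to 38% of the interaction was removed, in line with the algebra.

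In the common-link case, adjustment erases a real total effect in secure children. That would help produce the non-significant secure-group result that the Protocol predicts.

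**The case against.** The strongest reply is that nothing in the stated analysis uses NEPSY. The Protocol calls it only a potential covariate and ties it to no model, and the Analyses section does not mention it. This stands. A reader might infer that the planned Hypothesis 1 test is biased; the documents do not support that, because its ANOVA contains no covariate.

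A reader might also infer that adjustment must pull the birth weight by attachment interaction towards zero. It does so only if the birth weight–NEPSY link differs by attachment. The Hypotheses section of the Combined protocol and SAP makes a difference plausible, since it proposes that postnatal care determines how fetal adversity affects neurodevelopment. Plausible is not established.

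Third, the size is wholly assumed. Reading any percentage above as an expected loss would go beyond the documents. The algebra also supposes no unmeasured common cause of NEPSY and outcome; such a cause could add bias in either direction.

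Fourth, it would be too strong to call NEPSY a pure consequence of birth weight. The Combined protocol and SAP treats low SES as a risk factor for growth restriction and relates SES to children's cognitive development, so a child's score may also carry background confounding. The cited evidence concerns cognition and IQ, not language subtests. This cuts both ways: a battery of which the Protocol says "we will focus on the language domain" is also a narrow stand-in for general IQ.

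What remains is that the one role given to NEPSY is a covariate role, the follow-up ANCOVAs are open-ended, and nothing ranks an adjusted result against an unadjusted one.

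**Conclusion.** The point holds conditionally. If NEPSY is entered in a birth-weight model, the main effect and the within-attachment slopes estimate at most a direct effect, because the documents themselves place cognition downstream of fetal growth. The share lost is a × b / c, about 3% to 80% over assumed paths, and zero if NEPSY is unrelated to the outcome or to birth weight. The interaction loses about 0% under a common birth weight–NEPSY link, and about 8% to 38% in the assumed case where that link exists only in insecure children. The Hypothesis 1 ANOVA as written is not affected. This is an inexpensive improvement to an unspecified option, not a fault in the main test.

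**What to change.** In the NEPSY paragraph and the Analyses section of the Protocol, state that models without NEPSY are the main analysis for all birth-weight effects and interactions. Add that NEPSY is used either as an outcome or in an analysis labelled as mediation (direct effect) or sensitivity, following the treatment already given to CASI. A complete ban on NEPSY as a model term is not needed, since the direct-effect step of a mediation analysis includes it.

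If the worry is background confounding, adjust for family SES rather than for the child's ability at 72 months. SES addresses confounding; it does not measure ability. It would also help to describe the 72-month score as language ability rather than general IQ.

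The cost is one or two sentences, with no change to data collection.

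### Hypothesis 1 stratifies by gender to identify gender effects but names no test comparing the sexes, and its three birth-weight bands lose power if the effect is graded

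*Protocol*

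**What the plan says.** The Analyses section of the Protocol (the 72-month extension) opens: "In accordance with CIHR policy on identifying gender effects, analyses will be stratified by gender". It continues: "Statistical significance will be corrected for multiple comparisons where appropriate". It gives no alpha level and no list of the tests covered.

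Under Hypothesis 1 in the same section, the test is described as follows: "The results will be analyzed using a two way ANOVA (birth weight class) x attachment category". Gender is not a factor. The optional ANCOVAs that follow give sleep quality as their example of a moderator and do not name sex. Section IV (Statistical analysis) of the Combined protocol and SAP has a general rule that interaction tests assess effect modification; it does not name sex either.

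On coding: "Birth weight will be examined as a categorical variable using the following percentile groupings for birth weight for gestational age (0-20%, 21-40% and 41-70" per cent. The reason given is prior use: "We have previously used these groupings to show significant effects of birth weight on tests of attention and impulse control". Background and rationale says of attention that "the risk for inattention and ADD increases progressively as birth weight decreases", and then turns to anxiety and depression with "Although this issue has been less well clarified for other areas of psychopathology". For the DOMINIC-R, Measures says: "We will analyze the results for each subscale independently".

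**The concern.** The stated purpose of stratifying is to identify gender effects, yet the only analysis this implies is the same test run once in boys and once in girls. Each such test asks whether the birth weight by attachment interaction is zero in that sex. Neither asks whether the interaction differs between the sexes. If one is significant and the other is not, that can easily happen with no sex difference at all. The plan treats attachment properly, as an interaction to be tested, but gives sex no equivalent.

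The plan also leaves open whether a pooled test is run and which test is primary. That decides whether the central test of Hypothesis 1 uses all the children or half of them.

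The bands are a second, separate matter. They replace a continuous measure by three classes and a 1-df interaction by a 2-df one. That costs information where risk changes steadily with birth weight, which is what the plan says of inattention.

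**Working it through.** **Nothing to reproduce.** The plan gives no power, effect size or alpha for Hypothesis 1. It supports its sample size by comparison with published interaction studies. All power below is therefore conditional.

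**Inputs from the documents:** about 600 children enrolled; bands 0-20, 21-40 and 41-70; attachment secure or insecure.

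**Assumed:** equal numbers of boys and girls; 40% insecure; alpha 0.05 uncorrected; residual SD 1; percentiles spread evenly over 0-70 (SD of the reference z-score then 0.70); slope -0.25 outcome SD per population SD of birth weight in insecure children, none in secure children.

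**Step 1, pooled power.** Noncentrality of the continuous interaction = N x p(1-p) x Var(z) x slope² = 600 x 0.4 x 0.6 x 0.49 x 0.0625 = 4.4. On 1 df this gives 56% power. The bands keep about 82% of the information: 4.4 x 0.82 = 3.6, on 2 df, 38%. Within one sex the noncentrality halves to 1.8, giving 20%. Simulation (4,000 runs) gave 54%, 37% and 20%.

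| Case | Continuous, pooled | Bands, pooled | Bands, one sex |
|---|---|---|---|
| Central | 56% | 38% | 20% |
| Slope -0.20 to -0.30, 30-50% insecure | 35-73% | 23-53% | 13-29% |
| -0.25 per SD of the children analysed | 85% | 67% | 38% |
| N = 400 | 40% | 26% | 15% |
| Alpha 0.05/7 (the seven DOMINIC-R scales, as an example) | 28% | 15% | 6% |
| 0.5 SD step in the lowest band only | 59% | 68% | 38% |

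**Step 2, identical effects in both sexes.** With within-sex power a, exactly one sex is significant with probability 2a(1-a), and both with a². At a = 0.205: 2 x 0.205 x 0.795 = 0.326 and 0.205² = 0.042. The ratio is 2(1-a)/a, and it depends heavily on a:
- a = 0.66 (slope -0.50 in both sexes): about 1
- a = 0.38 (step case): about 3
- a = 0.205 (central): about 8
- a = 0.059 (alpha 0.05/7): about 32

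**Step 3, effect in one sex only.** Exactly one sex is then significant with probability 0.95a + 0.05(1-a), about 23% in the central case. This is below the 33% for identical effects. Setting 2a(1-a) equal to 0.05 + 0.90a gives a = 0.05 and a = 0.50, so that ordering holds only between those values. At a = 0.66 it reverses: 45% with identical effects, 64% with an effect in one sex.

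**Step 4, no effect in either sex.** At least one of two tests at 0.05 is significant with probability 1 - 0.95² = 9.75%.

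**Step 5, the direct test.** The SE of the sex x birth weight x attachment term is 2/√(600 x 0.4 x 0.6 x 0.49) = 0.24, so its 95% CI is about ±0.47. Power for a slope of -0.25 in one sex only is Φ(0.25/0.238 - 1.96) = Φ(-0.91), about 18%. With equal slopes in both sexes it is significant in 5%.

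**The case against.** The plan never says it will conclude a gender effect because one sex reaches significance and the other does not. A reader might infer that from the stratification sentence, but the documents do not state it, and the CIHR policy it refers to is not reproduced. The supportable statement is that the plan does not say how the sexes will be compared. The general rule on interaction tests in the 2004 document might be thought to fill the gap. It does show the investigators' approach to effect modification, but it does not mention sex.

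A reader might also take the halving of power as a property of the plan. It is not established. The ANOVA is written without gender and may be run pooled; the loss then does not arise.

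The banding has a stated reason, and the graded premise is given for inattention and ADD only. A claim that a continuous term is better for every outcome is unsupported: for the anxiety and depression scales the shape is unknown, and under a step the pooled bands win. The reply to the ethics committee at the front of the Protocol praises continuous exposures such as birth weight, but in the context of gene by environment work.

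Finally, the proposed three-way test is itself weak. That stands. It is a reason to report it as an estimate, not a reason to rely on separate tests, which do not address the question.

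**Conclusion.** The concern holds in a limited form and should be fixed. That separate tests by sex cannot show a sex difference is a matter of logic and does not depend on the assumed effect. Its size does. In the central case, identical effects produce a one-sex result in 33% of studies and a two-sex result in 4%, but that ratio runs from about 1 to about 32 as within-sex power falls from 66% to 6%. No single ratio should be quoted as typical, and one-sex results are not always more frequent under identical effects than under a true one-sex effect.

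If the stratified test is the one relied on, power drops from 38% to 20% (graded) or from 68% to 38% (step), with about 10% type I error across the two sexes. The banding loss, 56% to 38%, applies if the effect is graded, which the plan supports for attention outcomes only.

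These figures rest on assumed effect size, insecure share, alpha, attendance and effect shape. A reader might also infer that a large share of children above the 70th percentile is dropped. The birth-weight windows in the 2004 Methods suggest few such children, so this needs only a sentence of clarification.

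**What to change.** Change the analysis text for Hypothesis 1 as follows.
- Make one pooled model the primary test of birth weight x attachment, with sex as a covariate.
- Assess sex differences with a sex x birth weight x attachment term. Report sex-specific estimates with 95% CIs instead of separate significance tests by sex.
- At least for the attention outcomes (Conners and the DOMINIC-R ADHD scale), enter birth weight for gestational age as a continuous z-score from the same Canadian reference, with a pre-specified non-linearity check. Keep the pooled three-band ANOVA alongside it.

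This needs no new data. There are two costs. The three-way term has only about 18% power for the central one-sex effect and can exclude only large differences (CI about ±0.47), so it must be read as an estimate; a non-significant result is not evidence that the sexes are alike. The linear term also loses some power if only the lowest band is affected (59% against 68%), which is why the banded analysis should be kept.
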